Recruitment: A multipronged recruitment strategy will be used for this study. Recruitment will take place in late summer and fall of 2019. Interested students will be recruited through the weekly University announcement emails. The opportunity to participate will also be advertised on the Junior and Senior classes' social media pages. We will work with the UVM Office of Student and Community Relations to email students who live off campus and may be eligible for the study. Finally, we will set up tabling events in the Davis Center and in front of the library to reach interested students. Interested students will be directed to an online application that offers detailed information about the study and their responsibilities should they choose to participate. The application will also ask the applicant to complete a set of primary screening questions. Individuals who appear eligible based upon the initial screening questions will be invited to an in-person, group information session where they will receive detailed information about the study and informed consent will be distributed. Students will be instructed to carefully review the consent form and consult with anyone they feel can help them make a decision regarding participation. Students will be encouraged to take their time considering the study and to contact study personnel with any questions or concerns they have. Once a student has decided they would like to participate, they will be instructed to contact study personnel and arrange an individual meeting where they will review and sign consent with a member of the study team. If students wish to sign consent immediately following the information session, they will be instructed to wait until the information session has concluded and meet with a member of the study team in a separate office space to complete the consent process. Students will all finish the information session together and exit the meeting space. Only those interested in signing consent immediately will walk down the hall to the office space where the consent process will take place. There will be two exits from the information session meeting space (in Marsh Life Sciences) and there are multiple exits from the building, so students will not be exiting single file. These arrangements should ease pressure on students who are not ready to sign consent or who know they do not want to participate, even if a majority of students in attendance decide to sign consent.

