Following signed consent participants will be asked to complete a few baseline tasks to be fully eligible for participation in the study. These tasks include three days of food tracking using ASA-24, baseline surveys, submission of cooking frequency and food photos, and finally a one-on-one interview with study staff to discuss their participation. These baseline tasks are intended to ensure participant compliance and retention during the 18-week intervention.

Eligible participants will be assigned to one of four scheduled class periods based on their stated availability or recruited for the control condition. Once all classes are full, a random assignment table will be used to determine the group assignment for each class period. Participants will then be informed of their group assignment (active with follow up or active no follow up). Participants who are in the control condition will be randomly assigned to either a group that receives follow-ups or a group that does not. Groups will not be stratified by any criteria, and instead will be determined based upon participant availability.

Surveys will be administered through the study REDCap website at baseline and study end. Participants will receive links to the questionnaires and reminders to complete questionnaires via email. These measures are outlined in greater detail below. In addition to questionnaires, weekly data collection (Photo Elicitation and Cooking Frequency) will be administered through REDCap. Participants will receive a weekly email with links to a REDCap data collection tool. Participants will receive reminders to complete weekly data submissions, and will be given information regarding a helpline for using the study website and data entry.

Table 1 outlines when each measure will occur during the study.

Measures	Baseline	Weekly	Phase 1	Phase 2	Phase 3
ASA24					
HEI (calculated)					
CAFPAS					
Cooking Perceptions and Behaviors					
PSS					
Intuitive Eating Scale					
Interoceptive Awareness					
Cooking Frequency					
Photo Elicitation					
Class Evaluation					
Meal Kit Evaluation				X	
COVID-19 Questionnaire					X

Quantitative Measures

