A repeated measures ANOVA analysis will be used to compare changes in intuitive eating, diet quality and food agency over time both within the groups and between the groups. A generalized linear mixed model design will be used to compare the frequency of cooking at home each week over time and between the groups.

Aim 2: To evaluate if providing students with six weeks of a meal delivery service and then six weeks of recipes after completion of cooking classes maintains gains in diet quality, cooking frequency, intuitive eating, and food agency.

Hypothesis 2a: Meal delivery service will better maintain cooking frequency, intuitive eating skills, food agency and diet quality versus recipe provision only. Both meal delivery service and recipe provision will result in more frequent cooking, higher food agency, and higher diet quality the provision of no cooking support.

Hypothesis 2b: During both meal delivery service provision and recipe provision, those in the Cooking Class Condition will maintain higher levels of food agency, cooking frequency, and diet quality than those in the Control Condition.

Repeated measures ANOVA analyses will be used to compare between subjects effects from the meal delivery and recipe only interventions, as well as to compare the material support interventions against the control group. Repeated measures ANOVA will also be used to compare within subjects effects from end of fall semester to the end of each six-week material support intervention.

Aim 3: To positively influence participants' stress levels.

Hypothesis 3: Participants receiving cooking support will have lower scores on a measure of perceived stress than participants who do not receive cooking support. This will be true at all measurement time points.

A repeated measures ANOVA will be used to determine differences both between groups and over time in scores of perceived stress.

Aim 4: To explore the reasons why students cook or do not cook.

Hypothesis 4: There will be common themes defining why student choose to cook or not cook at home.

This is an exploratory aim, and qualitative analysis will be used to deduce popular themes.

Sample Size

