This is a pilot study with no previous data available to calculate expected statistical power. The sample size chosen was practical as our foods lab can only accommodate 16 people at a time. One group of each intervention arm (four) would give us data on approximately 64 subjects. This preliminary data will be used to determine the sample size power needed for a larger study with sufficient statistical power.

Inclusion/Exclusion Criteria: Eligibility and ineligibility criteria should be specific. Describe how eligibility will be determined and by whom. Changes to the eligibility criteria at a later phase of the research have the potential to invalidate the research.

Interested individuals will be directed to a study application that provides details about the study program and asks a series of screening questions. These questions are intended to determine basic eligibility for the study. Ineligible applicants will be notified of their ineligibility and directed to other campus resources related to cooking and meal planning. Eligible applicants will be directed to sign up for an in-person information session.

Inclusion criteria:

- Student at the University of Vermont
- Age 18-25
- Cooks dinner at home no more than 3x/week
- Access to a kitchen at home
- Lives independently off campus (may have roommates but may not live with guardians)
- Availability during scheduled cooking classes/demonstrations

Individuals will be excluded from the study if they do not complete baseline data collection measures prior to the first class meeting. Baseline data measures include four questionnaires (PSS, CAFPAS, Cooking Behavior, and intuitive eating scale), three days of ASA-24 logs, one photo elicitation survey, and one cooking frequency survey.

Inclusion of Minorities and Women: Describe efforts to include minorities and women. If either minorities or women are excluded, include a justification for the exclusion.

Women and minorities will be included. During recruitment, we will work with UVM Office of Student and Community Relations to ensure that our recruitment materials and procedures capture eligible students of all demographics.

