At the information session applicants will receive detailed information regarding the study interventions, the randomization process, and data collection procedures. During the information session designated staff who have been certified to obtain consent will discuss the informed consent form with the subject volunteer, reviewing each aspect of the consent form and allowing individuals to ask questions. This information session may be delivered in a group setting, although if scheduling does not permit engaging in the group session, the subject volunteer may be orientated individually. Potential participants often benefit from the group process in that they hear questions that others ask which may not have occurred to them but are of interest to them in their decision making about participation. Participants will be provided with a copy of the consent form at the group session but will not be asked to sign the form until they have had a chance to review the consent form fully. The person obtaining consent will be an individual who has been certified to obtain consent for the study and this person will thoroughly explain each element of the document and outline the risks and benefits, and follow-up requirements of the study. Participant privacy will be maintained and questions regarding participation will be answered. No coercion or undue influence will be used in the consent process. All signatures and dates will be obtained. A copy of the signed consent will be given to the participant. The informed consent process will be documented in each subject's research record.

Following informed consent, the remainder of screening will be conducted (e.g., self monitoring diary completed, discussion of randomization acceptance) and baseline data will be collected. Individuals who remain interested in the study after the session and have reviewed the consent form will be invited to complete baseline data collection online and then return for an individual screening session at which the remainder of the screening process will occur.

Control Condition

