At the conclusion of recruitment for the Cooking Class Condition, those who completed the initial application, but did not go farther in the recruitment process will be asked if they would like to participate in the control arm of the study. To participate, they will be asked to attend an Office Hours appt. with the PI or Study Coordinator to fill out informed consent and then will be given access to the baseline data collection online. Those in the Control Condition will also then be randomized to either receive meal kits and recipes in Phases 2 and 3 of the study, or to receive no further support. The contact information and screening information of participants who decline consent will be destroyed.

Information Withheld From Subjects: Will any information about the research purpose and design be withheld from potential or participating subjects? If so, explain and justify the non-disclosure and describe plans for post-study debriefing.

Not applicable

Attach full grant application, including budget information and/or any contract or draft

All materials must be submitted electronically to the IRB via InfoEd. Proper security access is needed to make electronic submissions. Visit the [InfoEd Resource Materials](#) page for more information.

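### Controls open baseline only after class recruitment has closed and no common baseline window is set, so class baselines will tend to be earlier and calendar drift can enter the Phase 1 contrasts

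*Combined protocol and SAP*

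**What the plan says.** **Order of recruitment.** Under Informed Consent, Control Condition, the control arm is filled second: "At the conclusion of recruitment for the Cooking Class Condition, those who completed the initial application" but did not continue are asked whether they would like to join as controls. They attend an appointment "to fill out informed consent and then will be given access to the baseline data collection online". No control baseline can therefore precede the end of class recruitment.

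**Class students.** Under Informed Consent, Cooking Class Condition: "Following informed consent, the remainder of screening will be conducted (e.g., self monitoring diary completed, discussion of randomization acceptance) and baseline data will be collected". The Procedures section makes the same tasks a condition of entry: "Following signed consent participants will be asked to complete a few baseline tasks to be fully eligible for participation in the study". Each class student's baseline is thus tied to that student's own consent, not to a calendar date.

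**Dates.** Procedures, Recruitment: "Recruitment will take place in late summer and fall of 2019". The Intervention section places Phase 1 in October 2019. The Inclusion/Exclusion Criteria supply the only limit on baseline timing, and it is a closing one: "Individuals will be excluded from the study if they do not complete baseline data collection measures prior to the first class meeting". No section gives an opening date or a window common to the arms.

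**Follow-up.** Questionnaires and dietary recalls are due at the end of each phase in all groups.

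**Analysis.** Statistical Considerations, Aim 1, uses repeated measures ANOVA to "compare changes in intuitive eating, diet quality and food agency over time both within the groups and between the groups". Cooking frequency has its own mixed model of weekly reports. Aim 3 analyses stress by repeated measures ANOVA, between groups and over time. None of these models includes assessment date or calendar week.

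**The concern.** A concurrent control arm earns its place by absorbing whatever would have happened anyway. For students, the move from late summer into mid-semester may by itself change diet, cooking and stress. That is an assumption, but a plausible one. The control arm cancels such drift only if both arms are measured over the same stretch of the year. Here the end of the interval is common to the arms and the start need not be. If class baselines sit earlier, the class arm's change includes some extra weeks of drift, and the analysis would read those weeks as a class effect or as the masking of one.

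This is distinct from the question of who enters each arm. Perfectly comparable students measured on different dates would still give a biased difference in change.

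**Working it through.** **The plan's own figure.** The sample size is 4 groups × 16 = 64, that is 32 class and 32 control students for the Phase 1 contrast. It was set by kitchen capacity. The plan says there were no data for a power calculation and states no alpha, SD or effect size, so what follows is illustrative.

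**Sequence.**
1. Class baseline follows each student's own consent, which occurs while class recruitment is open.
2. Control baseline follows control consent, which occurs after class recruitment has concluded.
3. Both must finish before the first class.
4. Late class recruits may still be doing baseline tasks when the first controls start, so some overlap is possible. Nothing in this sequence pushes control baselines earlier than class baselines.

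**Size of the gap (assumed dates).** Let W be the weeks from the first baseline to the first class, and c the weeks left for controls at the end. With baselines spread evenly in each arm:
- class mean = (W − c)/2
- control mean = W − c/2
- gap = W − c/2 − (W − c)/2 = W/2

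The value of c cancels, so the gap depends only on the assumed opening date and first class date:

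| Baseline opens | First class | W (weeks) | Mean gap (weeks) |
|---|---|---|---|
| 15 August | 1 October | 47/7 = 6.7 | 3.4 |
| 15 August | 15 October | 61/7 = 8.7 | 4.4 |
| 15 September | 1 October | 16/7 = 2.3 | 1.1 |

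A working range of about 1 to 4 weeks follows.

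**Bias.** Bias = drift per week × gap. Drift is assumed to be 0.025 to 0.05 SD per week:
- lowest: 0.025 × 1 = 0.025 SD
- highest: 0.05 × 4 = 0.20 SD

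**False-positive rate.** The SE of the difference in change, in SD units, is √(2(1 − r)) × √(2/32), where r is the assumed baseline to follow-up correlation:
- r = 0.5: 1.00 × 0.25 = 0.25
- r = 0.7: 0.775 × 0.25 = 0.194

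Two-sided rejection at an assumed 5% level is 1 − Φ(1.96 − bias/SE) + Φ(−1.96 − bias/SE):

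| Gap (weeks) | Drift (SD/week) | Bias (SD) | r = 0.5 | r = 0.7 |
|---|---|---|---|---|
| 1 | 0.025 | 0.025 | 5.1% | 5.2% |
| 1 | 0.05 | 0.05 | 5.5% | 5.8% |
| 4 | 0.025 | 0.10 | 6.9% | 8.1% |
| 4 | 0.05 | 0.20 | 12.6% | 17.8% |

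For scale, the difference detectable with 80% power at r = 0.5 is (1.96 + 0.84) × 0.25 = 0.70 SD.

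**Which outcomes are exposed.** Diet quality, food agency and intuitive eating are analysed as change from baseline and are fully exposed. Stress is exposed only in the over-time part of its ANOVA. Cooking frequency is modelled from weekly reports gathered during the phases, in the same weeks for both arms, so only its single baseline survey is exposed.

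**The case against.** The strongest reply is that the documents date no baseline in either arm. Recruitment opening is not baseline opening: an application, an information session and consent come first, and one recruitment passage allows at least a week before consent is signed. If baseline in practice opened in mid-September, the mean gap would be about a week and the bias close to nothing. The drift rate is also assumed, as is its running in one direction. All of this stands, and it is why the numbers above are a range and not an estimate.

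Second, the plan does not describe allocation consistently. The Study Design section randomizes all 64 students to classes or control, and the Procedures section says "Eligible participants will be assigned to one of four scheduled class periods based on their stated availability or recruited for the control condition". If everyone completed baseline before a single randomization, there would be no systematic gap. But the consent section is the only place that says how controls are approached, and it makes them sequential. The conflict needs reconciling; it does not remove the point.

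Third, this is a pilot sized by kitchen space, and the selection of controls from applicants who did not proceed is the larger threat to the class comparison. Both remarks are fair. They bear on priority, not on whether baselines should be aligned.

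A reader might go further and infer that class baselines do fall earlier by a known amount, or that every baseline-to-Phase-1 contrast is biased. The documents support neither. The ordering is a tendency, with overlap possible. Cooking frequency rests on weekly data from the phases. Hypothesis 3 mainly predicts stress levels at each time point, and the Phase 1 level is taken at the same point in every group.

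**Conclusion.** The concern holds in a limited form. Followed as written, the plan tends to place class baselines earlier than control baselines, and it neither prevents this nor records or adjusts for it. The closing limit bounds the gap without removing it. The affected results are the between-arm changes to the end of Phase 1 in diet quality, food agency and intuitive eating, the over-time part of the stress analysis, and the single baseline cooking-frequency survey.

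Size and direction cannot be determined from the documents. Under the assumed dates, drift and correlations, the bias is about 0.03 to 0.2 SD, with a false-positive rate between about 5% and about 18%, or a comparable masking of a real effect. The upper end needs baseline to open in mid-August and drift of 0.05 SD per week. The lower end is negligible.

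**What to change.** Collect baseline measures for all four groups in one common calendar window before the first class, for example the last two weeks. Hold class students' baseline tasks until the window opens, and invite controls early enough that they have consented before it does. End-of-phase timing is already common to the groups and needs no change.

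The cost is a scheduling rule. Early recruits wait between consent and baseline, and staff have less time to chase late tasks.

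The protocol pages carry an April 2020 approval stamp, so baselines have probably been collected already. In that case, report the distribution of baseline dates by arm and state the limitation. Adjustment for baseline week, or restriction to dates that both arms share, can be offered only as a sensitivity analysis: if the arms barely overlap in time, date is nearly collinear with arm, adjustment is extrapolation, and the restricted set may be almost empty.

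Aligning baselines does not cure the separate problem that controls are drawn from applicants who did not proceed. The sections that describe randomization of all 64 students still have to be reconciled with the sequential recruitment of controls.

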With the rise in obesity in America correlating strongly with the decline in the frequency that Americans cook at home, cooking may be an important behavior to encourage to promote health. Increasing the prevalence of Americans who cook meals at home may be an important health behavior to target, because cooking at home is widely regarded as being healthier than consuming food away from home. While interventions are limited in number and scope, the positive benefits of cooking at home on dietary quality seem to cut across age groups and populations from college students to older adults.^{6,7} Cooking classes may be an important intervention target because they may increase one’s food agency. Thinking of cooking as a health behavior, cooking classes may be equivalent to exercise classes for someone trying to increase their physical activity. The exercise classes give one the skills, social structure, and self-efficacy to begin exercising on one’s own. This study is designed to test whether cooking classes could do the same for someone’s food agency and cooking frequency.

The proposed pilot study is a trial to evaluate whether cooking classes produce greater gains in cooking skills and food agency compared to a control condition that does not receive cooking classes, as well as whether provision of meal delivery and recipes result in more frequent cooking than no meal delivery or recipes. There will be three phases to the study intervention and four study conditions. All conditions will receive 6 weeks of cooking classes, either active or demonstration, and two conditions will also receive a continued intervention including 6 weeks of meal kit delivery service followed by another 6 weeks of recipe provision.

Phase 1- Cooking classes or control condition. All participants in the cooking classes condition will attend 1 kitchen intensive session followed by 1 cooking class per week for 6 weeks. Control condition participants will receive no cooking instruction.

Phase 2- Meal Kits. Assigned participants will receive meal kit deliveries once per week for 6 weeks.

Phase 3- Recipes. Assigned participants will receive 5 healthy recipes by email once per week for 6 weeks.

We will randomize 64 students to one of four intervention conditions.

Group A (n=16) - Active cooking classes followed by meal kits and recipes

Group B (n=16) - Active cooking classes followed by no further instruction

Group C (n=16) – Control condition followed by meal kits and recipes

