Hypothesis 3: Participants receiving cooking support will have lower scores on a measure of perceived stress than participants who do not receive cooking support. This will be true at all measurement time points.

Aim 4: To explore the reasons why students cook or do not cook.

Hypothesis 4: There will be common themes defining why student choose to cook or not cook at home.

Study Design: Describe the research design, including a description of any new methodology and its advantage over existing methodologies.

We propose a randomized trial to evaluate whether cooking classes produce greater gains in cooking skills and food agency compared to a control condition, as well as whether provision of meal delivery and recipes result in more frequent cooking than no meal delivery or recipe provision. We will randomize 64 students to either the intervention condition where they will take part in six weeks of hands on cooking classes, or the control condition where they will receive no cooking instruction during the fall semester. Following the completion of cooking classes and the start of the spring semester, one active cooking (treatment) group and one control group will receive another 12 weeks of intervention while the other two groups will receive no further instruction. The two continued intervention groups will be subscribed to a meal delivery service for six weeks, and then receive only recipes for another six weeks. Assessments will be conducted at baseline and following each phase of the intervention for all groups.

Study Population

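### Cooking classes versus control is called randomised, but the procedure contains no random draw between them; only follow-up support versus none is allocated at random

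*Combined protocol and SAP*

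**What the plan says.** Two places describe allocation as random. The opening summary states: "We will randomize 64 students to one of four intervention conditions". Study Design states: "We will randomize 64 students to either the intervention condition where they will take part in six weeks of hands on cooking classes", and the sentence goes on to name the control condition as the alternative.

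The operative text differs. Under Procedures, in the paragraphs on baseline tasks and assignment: "Eligible participants will be assigned to one of four scheduled class periods based on their stated availability or recruited for the control condition". Once the classes are full, "a random assignment table will be used to determine the group assignment for each class period". The results of that table are then given: "Participants will then be informed of their group assignment (active with follow up or active no follow up". For the other side: "Participants who are in the control condition will be randomly assigned to either a group that receives follow-ups or a group that does not". The same paragraph adds that groups are not stratified and follow from when participants are available.

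Under Informed Consent, Consent Procedures, Control Condition, controls are sought after recruitment for the classes has ended, and the source is applicants who went no further: "those who completed the initial application, but did not go farther in the recruitment process will be asked if they would like to participate". They are then randomised to kits and recipes or to nothing further.

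The opening summary also contains a sentence that does not fit a control without instruction: "All conditions will receive 6 weeks of cooking classes, either active or demonstration".

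**The concern.** A reader of the summary and Study Design would take the effect of the classes as randomised evidence. The procedure instead lets entry to the class side or the control side depend on how far an applicant went in recruitment and on when the person was approached.

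The contrast matters because it carries much of the plan. It is Aim 1 (Hypothesis 1.1, numbered 1 under Statistical Considerations) and it returns as Hypothesis 2b. It is also Hypothesis 3 at the end of Phase 1, when classes are the only support anyone has received. If allocation was not random, a difference between the sides may reflect who joined by which route. The plan nowhere says that its two factors, classes and follow-up support, carry different evidential weight.

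**Working it through.** **1. Sample size.** Four groups of 16 give 4 × 16 = 64, which reproduces the plan's figure. The class contrast is A+B versus C+D, 32 versus 32. The support contrast is A+C versus B+D, also 32 versus 32. The plan gives no power calculation.

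**2. Every random draw in the documents.**

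| Contrast | Random step described? | Unit | Possible results |
|---|---|---|---|
| A versus B | Yes (Procedures) | Class period | Active with or without follow-up |
| C versus D | Yes (Procedures; Control Condition consent text) | Participant | Support or none |
| A+B versus C+D | None found | – | – |

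**3. Other mentions of randomisation.** Subject Selection speaks of people being enrolled and randomised but gives no mechanism. The consent text on the randomisation process and its acceptance stands under Cooking Class Condition and fits the A versus B draw. Neither supplies the missing step.

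**4. Documented differences between the sides.** These include:
- the timing of approach;
- progress beyond the online application;
- an information session and an individual screening session for the class side, against an office-hours appointment for controls (Consent Procedures);
- an incentive for completing baseline measures, given to controls only (Follow-up Data Collection).

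**5. The A versus B draw.** The table is applied to class periods already filled by availability. Four periods split two and two allow C(4,2) = 6 allocations. Two periods of 16 would allow 2. The documents do not state the number of periods per group.

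**6. What the planned analyses remove.** For Aim 1's continuous outcomes, repeated measures ANOVA compares change, so a stable baseline gap cancels. Differing trends and regression to the mean do not. Hypotheses 2b and 3 are worded as levels. The Aim 2 analysis uses between-subjects effects and within-subject change from the end of the fall semester, which is after the classes. There even a stable gap need not cancel.

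**7. Illustration for Aim 1's continuous outcomes only.** All inputs are assumptions: one normal pre-post outcome, 32 versus 32, no class effect, baseline gap d in SD units, pre-post correlation r. The change analysis and a baseline-adjusted analysis differ by (1 − r)d:
- d = 0.3: 0.21, 0.15 and 0.09 SD for r = 0.3, 0.5 and 0.7;
- d = 0.5: 0.35, 0.25 and 0.15 SD.

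Simulated false-positive rates at r = 0.5, for a nominal 5% test (d = 0.3 / d = 0.5):

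| | Change analysis | Baseline-adjusted |
|---|---|---|
| Gap persists | 5.2% / 4.9% | 10.2% / 19.1% |
| Gap shrinks to a common mean | 9.2% / 16.8% | 5.0% / 5.1% |

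Over r = 0.7 to 0.3, the biased analysis rejects in 7.5–13.6% (d = 0.3) or 12.9–28.1% (d = 0.5) if the gap persists. If it shrinks, the ranges are 7.5–11.0% or 11.2–21.8%. Neither analysis is better in general.

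**8. A baseline table cannot settle it.** The standard error of a baseline difference is √(2/32) = 0.25 SD, so the 95% half-width is 1.999 × 0.25 = 0.50 SD. A true gap of 0.3 or 0.5 SD would be significant 21.9% or 50.4% of the time. Under real randomisation a gap of at least 0.3 SD would arise by chance 23.0% of the time.

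**The case against.** The strongest reply is that Study Design is right and the procedural text is merely incomplete. That cannot be excluded, and the fix allows for it, but the sections conflict either way. The summary's sentence giving every condition classes or demonstrations suggests that some wording may be left over from a different design, so the summary is not the safer guide.

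It can also be said that this is an unpowered pilot, that no aim is named primary, and that the procedure is openly disclosed. All three are true. Pilot status excuses low power, not a label that the procedure does not support, and the plan intends these data to inform the sample size of a larger study.

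There is some mitigation. Both sides face the same limit on home cooking and must complete the same baseline tasks or be excluded (Inclusion/Exclusion Criteria). This may narrow a motivation gap. It does not restore randomisation.

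Two stronger readings are tempting:
- A reader might infer that controls are less motivated and that the class effect is therefore inflated. The documents report no baseline comparison, and the illustration shows bias in either direction depending on how a gap evolves.
- A reader might infer that the whole trial is non-randomised. Support versus none does have a random step on both sides, though in the class arm it is limited to a few class periods.

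**Conclusion.** The point stands and must be fixed. The documents claim random allocation between classes and control, and the procedure they describe has none. This rests on the text alone. It affects Hypotheses 1 and 2b, and 3 where support means classes.

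The size and direction of any bias are unknown. The figures in the working depend on assumed gaps and correlations. They do not represent weekly cooking frequency, clustering by class period or dropout, and they are not the reason for the severity. No planned number changes; what changes is what Aim 1 can conclude.

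**What to change.** Required:
1. Reconcile the opening summary and Study Design with Procedures and the Control Condition consent text. As the procedure stands, describe classes versus control as a non-randomised concurrent comparison, with controls recruited after the class arm from applicants who did not proceed. If a random step was in fact used, describe it in those two procedural places.
2. Confine randomised claims to support versus none. C versus D is allocated by individual. A versus B is allocation of a few class periods filled by availability. State the number of periods per group and that this is cluster-level allocation.
3. Do not treat the class effect as a randomised estimate in conclusions or in planning the larger study.

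Optional: beside the planned analysis, report a sensitivity analysis that regresses the follow-up outcome on class, baseline outcome and baseline cooking frequency, or uses the equivalent covariate-by-time terms. Covariate main effects alone leave the group-by-time term unchanged in complete pre-post data. Weekly cooking frequency would need its own model. Fix the analysis before data release and label it as specified after Phase 1, since Phase 1 was set for October 2019 and this version is stamped 4/14/2020. Show baseline standardised differences with intervals, and state that neither analysis removes unmeasured motivation.

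Cost: the required items are wording only, with no new data and no re-randomisation. The real price is a weaker causal claim for Aim 1. The optional analysis uses baseline measures already required, but means additional models for each outcome and follow-up assessment.
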